7.2 NULL AND ALTERNATIVE HYPOTHESES

No formal hypothesis testing is planned in this trial. All analyses in this trial are descriptive and exploratory.

7.3 PLANNED ANALYSES

No per protocol set will be used in the analysis. However, important protocol deviations will be summarised. The TSAP will specify the important protocol deviations in detail.

For the determination of the MTD, only MTD evaluable patients will be considered. For the analysis of secondary and further endpoints, all patients in the treated set (i.e. patients treated with at least one dose of trial medication) will be included in the analysis. Any other analysis sets will be defined in the TSAP.

7.3.1 General considerations

Treated set includes all patients who were treated with at least one dose of trial medication. The pharmacokinetic parameters listed in Sections [2.1.3](#) and [2.2.2](#) will be calculated according to the BI SOP ‘Standards and processes for analyses performed within Clinical Pharmacokinetics/Pharmacodynamics’ ([001-MCS-36-472](#)). PK analyses will be performed using validated software programs, normally, Phoenix WinNonlin [REDACTED] with applications validated for the respective purpose. Graphs and tables will be generated using validated customised [REDACTED] macros or appropriate graphic software.

[figure not shown]
7.3.2 Primary endpoint analyses

In order to identify the MTD, the number of patients with DLTs during the MTD evaluation period of Part I and Part II at each dose level must be presented. Patients who discontinue during the first treatment course for reasons other than DLTs will be excluded from the determination of MTD.

In addition, the number of patients with DLTs that occurred during the entire treatment period will be also summarised.

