3.3.4.1 Discontinuation of trial treatment

An individual patient will discontinue trial treatment if:

- The patient wants to discontinue trial treatment, without the need to justify the decision.
- The patient has repeatedly shown to be non-compliant with important trial procedures and, in the opinion of both, the investigator and sponsor representative, is not willing or able to adhere to the trial requirements in the future.
- The patient needs to use concomitant medication that interferes with the investigational medicinal product or trial assessments. Refer to Section [4.2.2.1](#) for prohibited concomitant medications.
- The patient can no longer receive trial treatment for medical reasons (such as surgery, adverse events, other diseases, or pregnancy). Refer to Section [4.1.6](#) for AEs that require treatment discontinuation.
- The patient experiences unequivocal PD by RECIST v1.1 and/or iRECIST (iRECIST applies to Part II only). Refer to Section [5.1.1](#) for details.

Even if the trial treatment is discontinued, the patient remains in the trial and, will undergo the procedures for the end of treatment (EoT) visit and follow up as outlined in the [Flow Chart](#) and Section [6.2.3](#).

For all patients the reason for withdrawal from trial treatment (e.g. AEs) must be recorded in the CRF. These data will be included in the trial database and reported.

During the dose finding part, patients withdrawn for a reason other than having a DLT or patients who miss more than one visit during MTD evaluation period may be replaced after discussion in the SMC if the information that needed to be collected during that visit is not available and makes the patient non-evaluable for the PK analyses or safety parameters (including evaluation for DLTs).

Patients who come off trial due to a DLT will not be replaced.

If a patient should become pregnant during the trial, the study treatment must be immediately stopped. The patient will be followed up until delivery or termination of pregnancy (see Section [5.2.9.2.3](#) for information on pregnancy forms). The data of the patient will be collected and reported in the electronic case report form (eCRF) until the last patient's last visit and any events occurring thereafter will be reported in the BI drug safety database.

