4.1.6 Dose modifications

Before initiating a new treatment cycle, the actual health status will be assessed according to [Flow Chart](#) and described in Section [5.2](#). To continue treatment with further cycles, all of the following retreatment criteria must be met:

- No uncontrolled hypertension (according to Exclusion-Criterion #10)
- QTcF ≤ 470 ms (according to Exclusion-Criterion #9)
- Acceptable tolerability (in case of an adverse event at the planned start of a treatment cycle patients may continue therapy only after recovery to a level which would allow further therapy; i.e. CTCAE grade 1 or pre-treatment value or considered not clinically significant)

In case one of the above mentioned criteria is not fulfilled the patient the administration of study drug(s) should be delayed. Any case of a delay in treatment cycle for more than 2 weeks should be communicated to the study team at Boehringer Ingelheim. The investigator in agreement with the BI study team will decide about further treatment of individual patient, based on known risk/benefit of BI 836880 and BI 754091.

In case an administration is delayed due to an AE, the patient should visit the site at least once a week for assessment of safety laboratory and AEs. More frequent visits may be appropriate as assessed by the Investigator.

Administration of trial drugs has to be stopped temporarily in case of a DLT (see Section [4.1.7](#)). Patients may resume the treatment only after recovery from DLT to at least fulfil retreatment criteria. The future dose of BI 836880 must be a tested dose which is one dose level below the dose received by the patient. The dose level for treatment resumption should

be as prescribed in [Table 4.1.6: 1](#). Treatment has to be discontinued in case the DLT is not reversible.

If a patient develops an interstitial lung disease, the treatment has to be discontinued.

Table 4.1.6: 1

Dose reduction recommendations for BI 836880

BI 836880 received dose	BI 836880 reduced dose
720 mg	360 mg
360 mg	120 mg
120 mg	120 mg (no change)

Dose reduction for BI 754091 is not allowed. The dose of BI 754091 may be delayed for a patient for one cycle, plus an additional 3 weeks (i.e. for up to 6 weeks), because of AEs following discussion with the sponsor.

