4.1.8 Definition of evaluable patient

For decisions on dose escalation, an evaluable patient is defined as a patient who has received BI 836880 or BI 836880 plus BI 754091 and either:

- has completed cycle 1 without experiencing DLT

OR

- has experienced DLT during cycle 1

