6.3 SUBJECT SETS ANALYSED

Treated set (TS) in monotherapy:

This patient set includes all patients enrolled in the trial who were documented to have administrated at least one dose of BI 836880 monotherapy. The TS is used for both efficacy analysis and safety analyses.

Treated set (TS) in combination therapy:

This patient set includes all patients enrolled in the trial who were documented to have administrated at least one dose of BI 836880 and ezabenlimab combination therapy. The TS is used for both efficacy analysis and safety analyses.

Dose escalation cohort treated set in monotherapy:

This patient set includes all patients enrolled in dose escalation cohort of monotherapy who were documented to have administrated at least one dose of study medication and were evaluable for the MTD determination. This set is used for dose finding and MTD determination in Part I.

Dose escalation cohort treated set in combination therapy:

This patient set includes all patients enrolled in dose escalation cohort of combination therapy who were documented to have administrated at least one dose of study medication and were evaluable for the MTD determination. This set is used for dose finding and MTD determination in Part II.

PK parameter analysis set (PKS)

The PK parameter analysis set (PKS) includes all subjects from the TS who provide at least one PK parameter that is not excluded.

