7.4 PRIMARY ENDPOINT

In part I and II, the primary endpoint is to assess the MTD based on the number of patients presenting DLTs during the MTD evaluation period. The primary analysis is for the determination of the MTD. The purpose of this analysis is to summarize and document the data that led to the selection of the MTD. Therefore, an overall summary of DLTs (see CTP Section 4.1.7 for the definition of DLTs) which occurred during the MTD evaluation period will be provided for each dose cohort from the dose finding cohort treated set. Patients, if any, who did not complete the MTD evaluation period for reasons other than DLT will be excluded from the analysis of the primary endpoint.

A summary of the number of patients with DLTs overall in any cycle will be also given by initial treatment and displayed in a similar format to the summary of DLTs occurring in the MTD evaluation period.

The analysis of the MTD is based on a Bayesian logistic regression model (BLRM) guided by the escalation with overdose control principle. The MTD is defined as the highest dose for a given schedule that is expected to cause less than 25% risk of the true DLT rate being above or equal to 33% during the MTD evaluation period. Estimation of the MTD during the dose escalation phase of the study will be based upon the estimation of the posterior probability of the incidence of DLT in toxicity categories during the MTD evaluation period for all evaluable patients. The model to be used is specified in CTP Section 7.

The posterior probabilities that the toxicity rates of each dose level fall into the categories specified in CTP Section 7 will be displayed.

[figure not shown]

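### The primary-analysis exclusion is worded by reason for leaving cycle 1 and conflicts with the evaluable-patient definition; read literally, it drops a patient who had a DLT and then left for another reason

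*Protocol*

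**What the plan says.** Three places word the rule by the reason for leaving.

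- Protocol 7.3.2: "Patients who discontinue during the first treatment course for reasons other than DLTs will be excluded from the determination of MTD".
- SAP 7.4: patients "who did not complete the MTD evaluation period for reasons other than DLT will be excluded from the analysis of the primary endpoint".
- Protocol 3.3.4.1, on replacement: the patients who may be replaced include "patients withdrawn for a reason other than having a DLT".

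Other places go by DLT status or by evaluability.

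- Protocol 4.1.8 opens with "For decisions on dose escalation, an evaluable patient is defined as a patient who has received" study drug. It then accepts either completion of cycle 1 without a DLT or a patient who "has experienced DLT during cycle 1". No condition is placed on what happens after the DLT.
- Protocol 3.1 updates the model once each patient in the cohort has either had a DLT or been observed for the MTD evaluation period.
- Protocol 7.3: "For the determination of the MTD, only MTD evaluable patients will be considered".
- SAP 6.3 builds its two MTD sets from treated patients who "were evaluable for the MTD determination". The SAP does not define evaluable itself.

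On treatment after a DLT, Protocol 4.1.6 requires a temporary stop and adds: "Patients may resume the treatment only after recovery from DLT to at least fulfil retreatment criteria".

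**The concern.** A DLT and the reason for leaving are separate facts. Drug is given on Day 1 of a 21-day cycle, and a reversible DLT leads to a pause, not an automatic exit. A patient could therefore have a DLT on Day 8 and leave on Day 16 because of progression or withdrawn consent. The reason for leaving is then not the DLT, although the DLT occurred inside the MTD evaluation period.

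Under 4.1.8 this patient counts. Under the words of 7.3.2 and SAP 7.4 the patient does not. The parts are small (about 9 and 15 patients are expected), and the loss runs in the unsafe direction for an overdose-control rule.

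**Working it through.** **1. The two rules side by side**

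| Course in cycle 1 | Protocol 4.1.8 | 7.3.2 and SAP 7.4, read literally |
|---|---|---|
| Completes, no DLT | evaluable | kept |
| DLT, completes the cycle | evaluable | kept |
| DLT, leaves because of it | evaluable | kept |
| No DLT, leaves for another reason | not evaluable | excluded |
| DLT, leaves for another reason | **evaluable** | **excluded** |

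The rules differ only in the last row. Protocol 7.3 and SAP 6.3 already limit the MTD determination to evaluable patients, so the fourth row is out before the exclusion sentence is reached. If evaluable carries its 4.1.8 meaning, the sentence either adds nothing or removes exactly the patients in the last row.

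**2. Direction**

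Removing one DLT patient changes r/n to (r − 1)/(n − 1). This is smaller than r/n whenever r < n, that is, whenever the dose level also has a DLT-free patient.

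**3. Sensitivity to one lost DLT (Part I)**

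Inputs:

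- the two-parameter logistic model of Protocol 7.1.1, logit(π) = log α + β·log(d/720);
- the mixture prior of Table 7.1.1: 2: weight 0.9 on means (−2.263, 0.116), SDs (0.677, 0.946), correlation −0.076; weight 0.1 on means (0.405, 1.323), SDs (2, 1), correlation 0;
- the EWOC limit P(π ≥ 0.33) < 0.25.

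The posterior was obtained by numerical integration on a grid.

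Reproduction of the plan's own figures:

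| Quantity | Printed | Recomputed |
|---|---|---|
| Prior at 360 mg, under/target/over | 0.925/0.049/0.026 | 0.923/0.050/0.027 |
| Prior at 720 mg, under/target/over | 0.751/0.169/0.080 | 0.750/0.170/0.081 |
| Scenario 6 (0/3 at 360 mg, 2/3 at 720 mg), over at 720 mg | 0.319 | 0.332 |
| Scenario 6, under/target/over at 360 mg | 0.865/0.114/0.021 | 0.867/0.112/0.020 |

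Scenario 6 with one of the two DLT patients dropped (0/3 at 360 mg, 1/2 at 720 mg):

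- P(overdose) at 720 mg falls from 0.332 to 0.104, from above the 0.25 limit to below it.
- P(target) is 0.260 at 720 mg and 0.059 at 360 mg, so the model's preferred level changes from 360 mg to 720 mg.

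These figures are illustrative. Not every Part I scenario reproduces from the printed prior: in scenario 3 the current-dose P(overdose) is 0.386 against a printed 0.241, and in scenario 5 it is 0.055 against 0.093. The Part II prior as printed gives 0.423 at 120/240 mg against 0.187 in Table 7.1.2: 6, so no Part II posterior is used.

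**4. Effect on the rate, under an assumption**

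The documents give no share q of DLT patients who would leave cycle 1 for another reason. If all other patients are evaluable and the true rate is p, the retained rate is p(1 − q)/(1 − pq). With p = 0.25:

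- q = 10%: 0.225/0.975 = 0.231 (−8% relative)
- q = 20%: 0.200/0.950 = 0.211 (−16%)
- q = 30%: 0.175/0.925 = 0.189 (−24%)

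For scale, 24 patients at a rate of 0.25 give 6 DLT patients, so these shares correspond to 0.6, 1.2 and 1.8 patients in the whole trial.

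**The case against.** The strongest reply is that the documents already give a consistent reading. Protocol 2.1.2, Protocol 7.3, SAP 6.3 and SAP 7.4 itself all base MTD estimation on evaluable patients. The only definition of evaluable is 4.1.8, which keeps the patient. Leaving for reasons other than a DLT can then be read as shorthand for leaving without one, and nothing says the test is a single reason entered on the case report form. This reading is reasonable and probably what was meant. It stands as a reason not to treat the loss of DLTs as settled. It does not remove the conflict: 4.1.8 is written for escalation decisions, the term MTD evaluable has no definition of its own, and a programmer following SAP 7.4 to the letter would drop the patient.

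A reader might infer three stronger things, and the documents do not support them.

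- **That cohort decisions would be made on depleted data.** Section 4.1.8 governs escalation expressly and 3.1 updates the model by DLT status; both count the patient. SAP 7.4 describes its analysis as documenting the data behind the MTD selection. The change of level in scenario 6 therefore shows how sensitive the model is, not what the plan would do.
- **That the patient would simply be replaced by a DLT-free one.** Replacement under 3.3.4.1 is optional, needs SMC discussion, and depends on missing information that makes the patient non-evaluable. A documented DLT makes the patient evaluable for DLT. Comparisons such as 2/3 with 1/3, or 1/3 with 0/3, need both a deletion and a replacement.
- **That the DLT would disappear from the report.** Both documents also summarise DLTs over all cycles. Protocol 4.1.7 and 5.2 use DLTs from all cycles, with a model re-run, for the RP2D. Protocol 7.3.2 limits its own exclusion to the MTD determination; only SAP 7.4 extends it to the whole primary endpoint.

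**Conclusion.** This is a real, unreconciled wording conflict between Protocol 7.3.2 and SAP 7.4 on one side and Protocol 4.1.8 on the other. It affects one kind of patient: a cycle-1 DLT followed by exit in the same cycle for a different reason. The exposure is mainly in the final primary analysis, where the literal rule would take the patient out of the MTD determination and, under SAP 7.4, out of the cycle-1 DLT summary. The bias would be downward wherever the dose level also has a DLT-free patient.

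The documents do not allow the frequency to be estimated, and the case may never arise. If it did, one patient could matter: in Part I scenario 6 the overdose probability moves from about 0.33 to about 0.10. That figure rests on the printed Part I prior, which reproduces this scenario but not all the others. The conclusion itself rests on the text.

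**What to change.** Replace the exclusion sentence in Protocol 7.3.2 and SAP 7.4 with: *Patients who do not complete the MTD evaluation period and have not experienced a DLT in it are excluded; any patient with a DLT in the MTD evaluation period is included, whatever the reason for discontinuation.*

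In Protocol 3.3.4.1, align the replacement wording with 4.1.8 by referring to patients *withdrawn without having had a DLT*, and state that a patient with a cycle-1 DLT is not replaced.

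The cost is about one sentence in each of three places, with no added patients, data or assessments. The SAP change should be made before database lock, so that the analysis sets are programmed from one rule.

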7.3.3 Secondary endpoint analyses

Please refer to Section [2.1.3](#) for PK related secondary endpoints. Details on the statistical inference for PK parameters, e.g., dose proportionality using C_{max} and AUC_{0-504h} of BI 836880 in case of more than 3 dose level tested, will be specified in the TSAP.

7.3.5 Safety analyses

Adverse events will be coded using the Medical Dictionary for Drug Regulatory Activities (MedDRA). Standard BI summary tables and listings will be produced. All adverse events with an onset between start of treatment and end of the REP, a period of 42 days after the last dose of trial medication, will be assigned to the on-treatment period for evaluation.

All treated patients will be included in the safety analysis. In general, safety analyses will be descriptive in nature and will be based on BI standards. No hypothesis testing is planned.

Statistical analysis and reporting of adverse events will concentrate on treatment-emergent adverse events, i.e. all adverse events occurring between start of treatment and end of the REP. Adverse events that start before first drug intake and deteriorate under treatment will also be considered as ‘treatment-emergent’.

Frequency, severity, and causal relationship of adverse events will be tabulated by system organ class and preferred term after coding according to the current version of the MedDRA at database lock.

Laboratory data will be analysed both quantitatively as well as qualitatively. The latter will be done via comparison of laboratory data to their reference ranges. Values outside the reference range as well as values defined as clinically relevant will be summarised. Treatment groups will be compared descriptively with regard to distribution parameters as well as with regard to frequency and percentage of patients with abnormal values or clinically relevant abnormal values.

Vital signs, physical examinations, or other safety-relevant data observed at screening, baseline, during the course of the trial and at the end-of-trial evaluation will be assessed with regard to possible changes compared to findings before start of treatment.

7.3.6 Interim Analyses

No formal interim analysis is foreseen.

The sponsor will continuously monitor the safety. The dose escalation design foresees that the sponsor and the SMC perform regular safety evaluations. These evaluations will be unblinded to dose.

If considered necessary, an evaluation of the efficacy and safety aspects will be performed. Results of this evaluation will be documented and archived. If applicable, such an analysis will be defined in more detail in the TSAP.

Regarding exploratory PK analysis, please refer Section [5.3.1](#).

7.4 HANDLING OF MISSING DATA

In general, no imputation will be performed on missing efficacy data. Detailed censoring rules will be specified in the TSAP. Missing baseline laboratory values will be imputed by the respective values from the screening visit. No other imputations will be performed on missing data although every effort will be made to obtain complete information on all AEs, with particular emphasis on potential DLTs. For partial or missing AE onset and/or end dates, BI internal rules will be followed (see Reference Document [001-MCG-156 RD-01](#) “Handling of missing and incomplete AE dates”).

Handling of missing PK data will be performed according to the relevant SOP of the Sponsor ([001-MCS-36-472 RD-01](#)).

7.5 RANDOMISATION

No randomisation will be performed.

7.6 DETERMINATION OF SAMPLE SIZE

No formal statistical power calculations of sample size were performed. Approximately 9 patients for Part I are expected, and approximately 15 patients for Part II are expected. As

Proprietary confidential information © 2019 Boehringer Ingelheim International GmbH or one or more of its affiliated companies

more patients might be needed based on the recommendation of the SMC and the actual number of cohorts tested.

8. INFORMED CONSENT, TRIAL RECORDS, DATA PROTECTION, PUBLICATION POLICY, AND ADMINISTRATIVE STRUCTURE

The trial will be carried out in compliance with the protocol, the ethical principles laid down in the Declaration of Helsinki, in accordance with the ICH Harmonized Guideline for Good Clinical Practice (GCP), relevant BI Standard Operating Procedures (SOPs), the Japanese GCP regulations (Ministry of Health and Welfare Ordinance No. 28, March 27, 1997) and other relevant regulations. Investigators and site staff must adhere to these principles. Deviation from the protocol, the principles of ICH GCP or applicable regulations as will be treated as "protocol deviation".

Standard medical care (prophylactic, diagnostic and therapeutic procedures) remains the responsibility of the treating physician of the patient.

The investigator will inform the sponsor immediately of any urgent safety measures taken to protect the trial patients against any immediate hazard, as well as of any serious breaches of the protocol or of ICH GCP.

The Boehringer Ingelheim transparency and publication policy can be found on the following web page: trials.boehringer-ingelheim.com. The rights of the investigator and of the sponsor with regard to publication of the results of this trial are described in the investigator contract. As a rule, no trial results should be published prior to finalisation of the Clinical Trial Report. In exceptional cases, data may be published before the clinical trial report as long as this is discussed and agreed to by the investigators and the sponsor.

The certificate of insurance cover is made available to the investigator and the patients, and is stored in the ISF.

